#### 10.1 Patient surveys

#### 10.1.1 Searches

Patient surveys will be conducted electronically in all 28 intervention and 28 control practices. Practice administrative staff will conduct searches of the clinical system for patients with a medication review code recorded in a specified time frame as detailed below. A bulk SMS text message will then be sent to the resulting list of patients using the Accurx system. The text message will include a link to an online survey; patients can contact their practice for a paper version if they wish. All GP clinical systems have the necessary functionality to carry out the required searches, and process evaluation practices will have been selected to ensure they have the necessary Accurx technology too. Conducting the searches and text messaging is relatively straightforward, but practice administrative staff will be provided with clear step-by-step instructions to help with the process. Although a relatively quick process, we will limit the number of times it is required to minimise the workload for practices. By using an established technology, we mitigate the risks associated with what is otherwise a relatively novel approach to carrying out this work.

#### 10.1.2 Response rates

Response rates to text messaging surveys can be as low as 10% in eneral population[38], but have been found to be substantially higher (>60%) for those associated with specific clinical care[39]. By ensuring surveys are very short, and it's clear to patients that it relates to a specific aspect of care delivered by their practice, we hope to maximise engagement. Smartphone usage is now widespread even in older patients. We therefore anticipate that response rates will still be reasonable, although will adjust for response bias in subsequent analyses (see 10.2.5 Analysis of survey data below).

#### 10.1.3 Patient experience survey

A patient survey will be sent to all patients who have received a medication review in the previous 2 weeks (i.e. around 15% of reviewed patients). Surveys will be conducted every 3 months during the 12-month intervention delivery period to assess the patient's experience of their review. By using a 2-

week limit, this should improve patient recall, and hopefully improve engagement. By conducting the survey at different time points, we will be able to see if patient experience varies over time (e.g. due to a learning effect or other change in practice). The patient experience survey will be built on existing instruments, including questions on shared decision making (CollaboRATE[41]), empathy (CaRE measure[42]), and both confidence and satisfaction (5-point Likert scales[13]). Patients will additionally be asked whether they are willing to be contacted separately to participate in an interview, as detailed above in section 5.2.4 Identification and recruitment of patient participants for interview. Electronic validation will be used to ensure response completeness in the electronic survey to reduce the risk of missing data.

#### 10.1.4 Quality of life survey

A further patient survey will be conducted at two time points to assess patient quality of life. This will be sent at 9 months to all patients receiving a review in the first 6 months of the intervention delivery period, and at 15 months to all patients receiving a review in the second 6 months of the intervention delivery period. This will provide quality of life measures (EQ-5D, EQ-VAS) and potentially additional relevant measures (e.g. treatment burden) at 3-9 months following the review. Again, we will be able to see if there is change over time between the first and second halves of the intervention delivery period. It is not straightforward to assess QoL at baseline, because it is not possible to know when the medication review will be carried out for a given patient. This prevents us conducting a full cost-effectiveness analysis, although it is still possible to undertake a cost-consequences analysis (see 12.0 Economic evaluation below).

#### 10.1.5 Analysis of survey data

A straightforward analysis will be conducted of findings, comparing outcomes (experience of care, quality of life) between trials arms, adjusting for key patient characteristics and clustering by practice. In particular, we will account for inclusivity and diversity by adjusting for patient factors such as deprivation and ethnicity, in our analyses. Quality of life measures will also be used in the economic evaluation. There is a potential for response bias in survey respondents. We will therefore capture core individual data on respondents in the survey that we predict to be associated with response rates, including age, gender, ethnicity, and education (this will be used as a proxy measure of socioeconomic status), in addition to morbidity status (from a core list of health conditions drawn from the Cambridge Multimorbidity Score), number of repeat medicines, and specific medications classes (based on BNF grouping).

At present, we are not certain whether we will be able to collect individual level data for non-responders: Accurx are currently undertaking development work which may allow this to be done. If available, we will use inverse-probability weighting to adjust for survey response rates. If individual non-response data are not available, we will still be able to get population data at each practice alongside the data from responders, and we use one of a number of alternative methods as summarised by Keeble [DOI: 10.4236/ojepi.2015.53020] to adjust for selection bias as a sensitivity analysis depending on the exact nature of the data available; this will be specified in the Statistical Analysis Plan.

#### 10.2 Qualitative interviews

We will conduct ~22 patient interviews (15 intervention, 7 control) within one month of review completion. Details of the approach for identification, invitation and recruitment are provided earlier. The survey will occur within 2 weeks of the patient's review, and patients will be invited for interview as

soon as possible after this to limit recall bias. Interviews will explore patients' views and experiences of the review in terms of content, delivery and outcomes, including preparedness, patient-centredness, shared decision making and acceptability.

We will also interview ~22 GPs and pharmacists from the 56 process evaluation practices (15 from intervention arm, 7 from control arm) with purposive sampling including for usage of the BRISMED Toolkit in the intervention arm. Interviews will explore practitioners' views/experiences of conducting reviews and identify what drives review content/delivery. Practitioners in the intervention arm will also be asked about their use of the BRISMED Toolkit, how it affected and informed their practice, and how they think it could be implemented nationally. Practitioners will be interviewed once the intervention delivery period has ended, to avoid the interview process influencing their views of the study and intervention.

Interviews will be semi-structured to ensure key areas are discussed, whilst allowing participants to raise issues they consider important. Separate topic guides will be developed in parallel for practitioner and patient interviews, including questions relevant to both interviewee groups, aiding cross-group comparisons. Interviews (~40 mins) will be conducted online or by phone. Data collection and analysis will proceed in parallel, with initial findings informing the focus of later interviews. Data collection will end when saturation is reached[43].

With participant consent, interviews will be audio recorded and transcribed verbatim. Data will be analysed thematically[44] to allow comparisons to be made within and across data sets, permitting identification of key themes, deviant cases, and differences/similarities in the views of patients, GPs and pharmacists. Two researchers will independently code a subset of transcripts, then discuss coding discrepancies to achieve consensus and maximise rigour. Throughout analysis, findings will be presented to the wider research team and PPI advisors to encourage reflection and ensure credibility. NVivo software will be used during data analysis to aid data management and to facilitate electronic coding and retrieval of data.

#### 10.3 Observations of medication review

Audio-recording of reviews will be undertaken in both trial arms to examine how reviews are conducted in practice, including how the BRISMED Toolkit is implemented and affects review content/delivery in intervention practices. This data collection method is less intrusive than in-person observation, so less likely to influence practitioner behaviour. We have successfully used this approach to evaluate reviews as part of our IMPPP polypharmacy trial.

We will ask clinicians to record 20 consecutive reviews conducted over a 2-week period in 10 intervention and 5 control practices (i.e. total 300 reviews); this simplifies logistics as no decisions need taken by the clinicians or research team with respect to which specific reviews should be recorded. We will vary the timing of this activity in different practices, to allow us to examine whether changes in practice occur over the intervention delivery period. From the 300 reviews recorded, we will then purposively sample up to 25 and 15 reviews from intervention/control arms respectively, with a mix of GPs and pharmacists, and within the intervention arm select recordings where the BRISMED Toolkit has been used (identification, recruitment and consent processes are detailed above within Recruitment procedures; Section Sampling and consent for observation of medication review).

Analysis will focus on the content/delivery of reviews, using conversation analysis techniques[45] to explore practitioner and patient interaction. A bespoke observation guide will be co-developed by the

research team and PPI advisors. Specific elements of this guide will focus on person-centred communication and associated behaviours, informed by questions from existing instruments (e.g. SDM-Q9[46], CollaboRATE[41], CaRE[42], 5-item OPTION[40]). When analysed alongside data from the patient/practitioner interviews, this will provide detailed understanding of how reviews are conducted in practice.

#### 10.4 Implementation evaluation

We will assess intervention implementation of the BRISMED Toolkit by examining rates of recorded medication review (including use of the BMR Model) using routine practice data extracted by the ORCHID system, and by distributing a short, practice-level survey to all participating intervention practices once intervention delivery ends. The practice-level survey will be used to capture data related to routinely used practices and processes for the organisation and delivery of reviews (i.e. usual care) including which professionals conduct reviews (e.g. GP, clinical Pharmacist), the mode of delivery of reviews (e.g. in-person, via telephone), type of review (e.g. structured medication review with the patient), content of review (e.g. patient perspectives, safety, medication use considerations) and use of tools or models to support delivery (e.g. Scottish 7-Steps, NO TEARS). Additionally, the practice-level survey administered to intervention practices will capture measures of engagement with the intervention to quantify the nature of implementation (e.g. number/type of clinicians involved, which elements of the BRISMED Toolkit were used). This will help understand differences in outcomes between trial arms.

#### 10.4.1 Assessment of fidelity

The BRISMED Toolkit comprises five key elements (review model, primer document, guidance documents, training materials, IT templates), and it will be possible to quantify usage of these within all the intervention sites. Implementation data for all intervention sites will be collected from several sources. Use of the training materials will be captured through login requests to the website and time spent on the website, providing us insight into which practices have accessed these materials and for how long. We will be able also to quantify use of other BRISMED Toolkit materials on the website by clinicians (e.g. downloads of primer, guidance documents, templates).

The IT templates given to intervention practices will be designed so that data recorded within the template is coded in a specific way within the clinical record (e.g. coded record identifying use of the BRISMED Toolkit). This information will then be extracted alongside other routine clinical practice data through the ORCHID network system. This will be possible in all intervention practices and not just the subset involved in the process evaluation.

Additionally, a practice-level survey will be administered to all intervention practices at the end of intervention delivery. The survey will capture information related to usage of each the five elements of the BRISMED Toolkit and the number and type of clinicians engaging with and using the intervention to support medication reviews.

#### 10.4.2 Analysis and reporting of fidelity

Descriptive analyses will be undertaken to categorise practices according to fidelity/implementation, for different aspects of BRISMED Toolkit usage (i.e. engagement in training, usage of BRISMED online materials and IT templates, responses to practice- level, end-of-study survey). Secondary analyses will then be undertaken to explore how effectiveness varies by degree of fidelity, providing mechanistic insights into intervention efficacy. However, the primary effectiveness analysis will be performed using the ITT principle to preserve randomisation and avoid baseline confounding; this analysis will not adjust for fidelity.

#### 11.0 Statistics and data analysis

#### 11.1 Sample size calculation

Based on baseline pilot data from our IMPPP trial evaluating primary care management of polypharmacy (NIHR ID 16/118/14), and previous data on the prevalence of STOPP/START indicators[31], we expect 40% of patients to be eligible for review, with a primary outcome rate of 20%. Work by Stocks[32] found an ICC of 0.04 for a composite potentially inappropriate prescribing (PIP) indicator in UK general practice. Two other studies using similar outcomes have found ICCs on the GP practice scale ranging from 0.01 to 0.025 [34] [35]. A Cochrane review found a mean risk reduction of 21% in PIP[33]. Based on more conservative values (RR=15%) and using the upper estimate of ICC on the GP practice scale (0.04), 250 PCNs per arm (mean±SD size 20593±15229, with 40% eligible) per arm provides 93.3% power (alpha=5%) to detect a meaningful 15% relative reduction in primary outcome.

We estimate that of those on medications, 76% of individuals will be receiving up to 6 regular medications. This makes no difference to the power we would have to detect an effect within this subgroup.

With practices undertaking 5000 reviews per year (40% review rate from an average of 12514 patients), surveys sent to half of patients receiving a review, and a survey response rate of 10%, we can anticipate ~250 responses to the QoL survey per practice. The coefficient of variation in ORCHID practice list size is around 0.68. The DREAMER medication review trial found a baseline EQ-VAS of 70 (SD 16)[36], and we estimate an ICC on the GP practice scale of 0.11 [37]. Based on an effect size of 5 points on the EQ-VAS, 28 practices per arm (total 56) will provide us with 80.8% power.

Sample size calculations have been carried out on the PCN scale for the main study which is the unit of randomisation. Sample size calculations for the process evaluation are carried out on the GP practice scale however we will ensure that only one GP practice per PCN can be randomised to the process evaluation to maintain independence within a PCN.

#### 11.2 Progression criteria

A single "stop-go" criterion related to practice recruitment is proposed, prior to intervention roll-out, to mitigate the risk associated with inadequate recruitment:

- ≥380 practices per arm (i.e. >80% power) proceed with intervention roll-out
- 300-379 practices per arm (i.e. >70% power) discuss with funder including either proceeding regardless, or extending recruitment for an additional 3 months
- <300 practices discuss termination of the study with funder, or restricting to the planned process
  evaluation analyses in the subgroup of 56 practices (this will still provide invaluable data into
  quality of life, treatment burden and other aspects of patient and clinician experience which will be
  extremely useful in its own right).

#### 11.3 Statistical analysis plan

The analysis and reporting of this trial will be undertaken in accordance with Consolidated Standards of Reporting Trials (CONSORT) guidelines, as extended to cluster trials. The statistical analyses will follow a pre-defined Statistical Analysis Plan (SAP) agreed with the TSC and DMC. The main primary

outcome comparative analyses between randomised arms will be conducted on an intention-to-treat (ITT) basis without imputation of missing data.

#### 11.3.1 Preliminary analyses

Descriptive statistics of baseline cluster level and individual level clinical and socio-demographic characteristics will be used to describe the study sample and to ascertain comparability of the randomisation groups.

#### 11.3.2 Main analysis – primary outcome measure

Our primary outcome will be potentially inappropriate prescribing (PIP). This will be a binary variable, including the widely used STOPP/START indicators (these are originally designed for assessing prescribing in the elderly, but many are still relevant to younger patients) and the most frequently occurring age-independent PIP indicators identified from our IMPPP trial. The potentially inappropriate prescribing indicators used in the IMPPP trial are well established and were previously successfully employed in the DQIP trial[21].

The primary analysis will use random effects Poisson regression on the practice scale to explore the rates of potentially inappropriate prescribing indicators within each GP practice at the end of the intervention period by arm using the ITT principle. The random effect will account for clustering by PCN. The number of patients potentially eligible for review at each GP site will be used as the offset term whilst also adjusting for the baseline rates of the outcome. We will determine baseline rates by looking at the electronic prescribing records at each GP site in the 12 months prior to randomisation. This will be a test for superiority focussing on the estimate, 95% CI and p-value from the regression model.

#### Additional analyses - primary outcome measure

Additional analyses of the primary outcome will include a subgroup analysis of patients receiving

≤6 regular medicines. Methods for subgroup analyses are described in the section below, 11.3.3.

This *a priori* subgroup analysis is proposed as there is evidence from our IMPPP trial that patients with fewer medicines may have greater benefit [currently unpublished], and that interventions focused on narrower aspects of prescribing safety (and thus potentially less complex patients, with fewer morbidities or medicines) show effectiveness [20,21].

#### 11.3.3 Secondary analyses

Analysis of the secondary outcomes will use the same method as for the primary outcome analysis. Subgroup analyses will be undertaken by age, sex, socioeconomic status, medication count, and evidence of implementation within practices (coded record identifying BMR Model). We will not fit different regression models for each subgroup, but instead will add an interaction term to the analysis model to derive the effect size within subgroups; this is more efficient and allows a hypothesis test of effect sizes being different in subgroups.

We will explore analyses on the individual level for the primary and some of the medication-related secondary analyses (e.g. medication count, MRCI). However, this approach is logistically problematic for the analysis of outcomes such as health service utilisation or medication adherence, which might take up to 12 months to become apparent. A considerable (i.e. 12-month) wait would be required after the intervention period ends for all the necessary data to become available. Analysis on the practice scale mitigates this issue.

Our analysis of quality of life and patient experience will be random effects regression models (linear, logistic or Poisson models, as appropriate) for each individual by arm using the ITT principle. A random effect will account for clustering by GP practice. This will be a test for superiority focussing on the estimate, 95% CI and p-value from the regression model.

Missing data is unlikely to be a significant issue for our main analyses, e.g. if a drug or disease is missing in routine data it is generally assumed that this corresponds to its absence rather than a recording omission, and it is generally difficult (and often impossible) to distinguish these two possibilities. Given the nature of routine health record data, other key factors such as age and gender are unlikely to be missing. We will explore the nature of missingness for other patient-level data such as ethnicity and socioeconomic deprivation, and use established approaches such as multiple imputation to address missingness if appropriate.

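### The implementation subgroup in section 11.3.3 cannot be tested by an arm interaction, because the code that defines it exists by design only in the intervention arm

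*Protocol*

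**What the plan says.** Section 11.3.3 names five subgroup variables: "Subgroup analyses will be undertaken by age, sex, socioeconomic status, medication count, and evidence of implementation within practices (coded record identifying BMR Model"). Four describe patients; the fifth describes what the practice did. One method is set for all five: separate models are ruled out, and the analysts "will add an interaction term to the analysis model to derive the effect size within subgroups". The reason given is that this is more efficient and "allows a hypothesis test of effect sizes being different in subgroups".

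Section 10.4.1 says where the code comes from: "The IT templates given to intervention practices will be designed so that data recorded within the template is coded in a specific way". It describes the result as a "coded record identifying use of the BRISMED Toolkit", and adds about its extraction: "This will be possible in all intervention practices and not just the subset involved in the process evaluation". Section 8.3 says that the templates are reached through a website whose link goes only to intervention practices. No control-arm counterpart of the code is defined.

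Section 5.2.1 leaves the manner of implementation to each practice and accepts that some intervention practices may not fully engage. Section 10.4.2 plans separate work on implementation: "Secondary analyses will then be undertaken to explore how effectiveness varies by degree of fidelity". It names no model for this. It keeps the primary analysis on the intention-to-treat principle, without adjustment for fidelity, so that randomisation protects that comparison.

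**The concern.** A subgroup interaction asks whether the difference between arms changes across levels of a characteristic. That requires both arms to be represented at each level. Age and sex meet this requirement; a code that only one arm can generate does not. Section 11.3.3 treats the two kinds of variable alike and promises an effect size within each subgroup and a test between them.

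The second difficulty is that implementation happens after allocation and is the practice's own decision. Even if some coefficient can be fitted, it does not compare groups formed by randomisation. Practices that take up the template may differ in organisation, staffing or prescribing trend from those that do not. At stake is the reading of a secondary analysis: a non-randomised contrast could be reported beside true subgroup effects as though it were one of them.

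**Working it through.** The plan gives no numerical figure for this analysis, so there is none to reproduce. The power statement in section 11.1 concerns the primary comparison and is not involved. The check is whether the stated model can be fitted.

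**Inputs**
- Arm, A: 0 for control, 1 for intervention.
- Implementation, I: 1 if the practice has the code, 0 if not (sections 10.4.1 and 11.3.3). I take the code named in 11.3.3 to be the template code of 10.4.1, since no other source is described.
- I = 0 for every control practice (sections 8.3 and 10.4.1).
- 412 practices per arm: section 6.0 equates 250 PCNs with 412 practices.
- Uptake in the intervention arm: not given. Assumed values of 30%, 50% and 80% were tried.

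**Model.** On the log-rate scale, leaving out the offset, baseline rate and PCN random effect:

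log rate = b0 + b1·A + b2·I + b3·A·I

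**Cell values**

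| Group | A | I | A·I | Log rate |
|---|---|---|---|---|
| Control, no code | 0 | 0 | 0 | b0 |
| Control, code | 0 | 1 | 0 | b0 + b2 (empty by design) |
| Intervention, no code | 1 | 0 | 0 | b0 + b1 |
| Intervention, code | 1 | 1 | 1 | b0 + b1 + b2 + b3 |

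Three occupied cells cannot identify four parameters. Where A = 0, both I and A·I are 0; where A = 1, A·I = I. The two columns are therefore identical, and only the sum b2 + b3 can be estimated.

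**Numerical confirmation.** The matrix [1, A, I, A·I] with 412 practices per arm had rank 3 of 4 at each assumed uptake (30%, 50% and 80%), with the I and A·I columns identical each time.

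The omitted terms do not help. A baseline-rate covariate adds one column and at most one to the rank, so the shortfall of one remains. The offset and the PCN random effect do not fill the empty cell. Grading implementation (for example, as the share of reviews coded) does not help either: it is still 0 in every control practice, so its product with arm still equals itself.

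**What remains estimable**
- b2 + b3: implementers against non-implementers within the intervention arm.
- b1: non-implementers against all controls.
- b1 + b2 + b3: implementers against all controls.

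The interaction b3 is not among them. Each of the three contrasts selects practices by what they did after randomisation. The model in section 11.3.2 adjusts for baseline PIP, which deals with differences in prior level. It does not deal with a difference in how PIP would have changed anyway.

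**The case against.** The strongest defence is that little depends on this item. It is one of five secondary subgroup variables, and section 10.4.2 already keeps the primary analysis free of fidelity and treats the fidelity work as exploratory. The planned model adjusts for baseline PIP, so confounding by prior prescribing level would be largely removed. Section 11.3 refers to a predefined SAP, not shown here, where coding and labelling might be settled. All of this bears on how serious the point is, and it stands to that extent. It does not rescue the stated method. Section 10.4.2 names no model and does not qualify section 11.3.3, which fixes one that cannot be fitted as described. This is not detail left to a later document.

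It could also be said that contamination might put a few codes into control practices. The term would then be estimable in a technical sense, but against a handful of stray sites that do not form a comparable control subgroup.

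Three stronger readings are tempting and are not supported:
- A reader might infer that the main result is compromised. It is not; the primary analysis does not use implementation.
- A reader might infer that a null toolkit would show a spurious benefit of some particular size among implementers. The documents give neither uptake nor any difference between adopters and others, and bias after baseline adjustment requires adopters to differ in PIP trend as well as level. No size should be quoted.
- A reader might infer that an instrumental-variable analysis is the required replacement. Section 10.4.1 lists five toolkit elements, and training, primer and guidance can act without a template code. Defining use by the code alone therefore strains the exclusion assumption.

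**Conclusion.** The point holds as a narrow, structural error in section 11.3.3. For the implementation variable, the stated interaction is aliased with the subgroup's main effect (rank 3 of 4), so the promised within-subgroup effect and hypothesis test cannot be obtained. The estimable contrasts are non-randomised and post-allocation.

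This rests on two readings: that the code in 11.3.3 is the template code of 10.4.1, and that control practices do not receive the template, as section 8.3 provides. It does not depend on uptake, the number of practices or the intraclass correlation. The other four subgroup variables can vary within both arms and do not share this fault. Section 10.4.2 is not itself wrong; it is the natural home for this analysis.

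**What to change.** Delete implementation from the interaction-based subgroup list in section 11.3.3 and refer the reader to section 10.4.2. There, specify an exploratory fidelity analysis that adjusts for baseline PIP, accounts for PCN clustering, names the contrast estimated and is labelled explicitly as non-randomised.

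Optionally, add a complier-average (instrumental-variable) estimate with randomised arm as the instrument. If so, state how toolkit use is defined, and say that the exclusion assumption is doubtful when use means the template code alone.

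The cost is a short change of wording in the protocol, carried into the SAP, plus one further model if the optional estimate is wanted. The data are already to be extracted. What is given up is an interaction test that could not have been carried out.

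### Subgroup interaction tests use a Poisson model whose only stated random effect is for PCN, so their standard errors are too small whenever the subgroup ratio varies between practices or PCNs

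*Protocol*

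**What the plan says.** Protocol section 11.3.2 sets the primary analysis as a Poisson regression of practice-level PIP rates. The offset is the number of patients eligible for review at each site, and the model adjusts for the site's baseline rate. One random term is stated: "The random effect will account for clustering by PCN".

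The additional analysis of the primary outcome, in patients on six or fewer regular medicines, has no model of its own: "Methods for subgroup analyses are described in the section below, 11.3.3". Section 11.3.3 lists age, sex, socioeconomic status, medication count and evidence of implementation as modifiers. It declines to fit separate models and "instead will add an interaction term to the analysis model to derive the effect size within subgroups". It presents this as more efficient and as allowing a test of whether effects differ between subgroups.

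The protocol names no practice-level random term, no subgroup random slope, no overdispersion parameter and no robust variance.

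**The concern.** The arm effect is a contrast between PCNs, and a PCN intercept is the right term to protect it. An arm-by-subgroup interaction for a patient-level modifier such as medication count is different. Each practice contributes patients to both subgroups, so the interaction compares the subgroup ratio within PCNs across arms. The PCN intercept, and a baseline rate taken for the whole site, are common to both subgroups and drop out of that ratio. What remains in the model is Poisson noise, which is very small with about 8,200 eligible patients per PCN. Real variation in the subgroup ratio from one practice or PCN to another has no variance term.

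The ≤6-medicines analysis was agreed with the Trial Steering Committee, and the protocol gives reasons why benefit may be greater in that group. A spuriously significant interaction in the anticipated direction would be easy to believe, and could influence who is prioritised for review.

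**Working it through.** **Step 1. Reproduce the plan's own figure.** The inputs are all in section 11.1:
- "we expect 40% of patients to be eligible for review, with a primary outcome rate of 20"%
- "250 PCNs per arm (mean±SD size 20593±15229, with 40% eligible")
- "using the upper estimate of ICC on the GP practice scale (0.04")

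Eligible per PCN: m = 20593 × 0.40 = 8,237. CV = 15229/20593 = 0.74.

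Design effect = 1 + ((CV² + 1)m − 1) × ICC = 510.6.

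Effective patients per arm = 250 × 8,237 / 510.6 ≈ 4,033. Power for 20% v 17% at two-sided 5% is 93.45%. The protocol says the design "provides 93.3% power (alpha=5%) to detect a meaningful 15% relative reduction in primary outcome", so the inputs are understood as intended.

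**Step 2. What the stated model gives as the interaction standard error.** Section 11.1 puts 76% of those on medication at six or fewer medicines. With a 20% rate in both groups (a simplification), events per arm are 250 × 8,237 × 0.76 × 0.20 ≈ 313,000 and 250 × 8,237 × 0.24 × 0.20 ≈ 98,800. The Poisson-only standard error is

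√[2 × (1/313,000 + 1/98,800)] ≈ 0.0052.

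Simulation of the stated model gave the same average model standard error, 0.0052.

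**Step 3. What the true sampling spread is.** An ICC at 20% prevalence implies a between-practice log-rate variance of ln(1 + 4 × ICC): 0.148 at ICC 0.04 and 0.039 at ICC 0.01. If the two subgroups' log rates correlate ρ across practices, their difference has variance 2(1 − ρ) times this. Section 6.0 gives 412 practices per 250 PCNs and section 11.1 a practice-size CV of 0.68, so each arm has about 412/(1 + 0.68²) ≈ 282 effective practices. At ICC 0.04 and ρ = 0.90:

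- contrast variance = 2 × 0.10 × 0.148 = 0.0297
- contribution to the interaction variance = 2 × 0.0297/282 = 0.000211
- sampling variance of a 20% binomial = 0.8 × 0.0052² ≈ 0.000021
- true SD = √0.000232 ≈ 0.0152, which is 0.0152/0.0052 ≈ 2.9 times the model's value

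**Step 4. Simulation.** There were 300 runs per row, with no true interaction, 500 PCNs, practice sizes as above, a site-level baseline covariate and a PCN random intercept only. The assumptions not in the protocol are ρ, a baseline-to-follow-up correlation of 0.8, and half the practice variance lying between PCNs.

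| ICC | ρ | True SD | Model SE | Ratio | False positives | With PCN-clustered robust SE |
|---|---|---|---|---|---|---|
| 0.01 | 1.00 | 0.0047 | 0.0052 | 0.92 | 3% | 6% |
| 0.01 | 0.95 | 0.0075 | 0.0052 | 1.45 | 17% | 6% |
| 0.01 | 0.90 | 0.0087 | 0.0052 | 1.68 | 21% | 5% |
| 0.04 | 1.00 | 0.0045 | 0.0052 | 0.88 | 2% | 6% |
| 0.04 | 0.95 | 0.0112 | 0.0052 | 2.18 | 39% | 4% |
| 0.04 | 0.90 | 0.0151 | 0.0052 | 2.94 | 49% | 4% |

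The simulation error is about 1 percentage point at 5% and 3 points at 40 to 50%. Replacing the site-level baseline by a subgroup-specific one, at ICC 0.04 and ρ = 0.90, gave ratios of 1.8 to 2.1 and 29 to 36% false positives.

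**Step 5. How little variation is needed.** Suppose instead that PIP is 13.7% in the ≤6-medicines group and 40% in the rest (assumed; it averages to 20%). An average PCN then has about 860 and 790 events. The Poisson variance of its log ratio is 1/860 + 1/790 ≈ 0.0024, an SD of about 0.05. A true spread of only about 5% between PCNs in the subgroup ratio doubles the variance the model allows for.

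**The case against.** Four points on the other side have force.

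**The size rests on unknowns.** The protocol gives neither ρ nor the split of variance between PCN and practice, and 0.04 is its upper ICC: "Two other studies using similar outcomes have found ICCs on the GP practice scale ranging from 0.01 to 0.025". A reader might infer that the standard errors are in general several times too small and that most significant interactions would be false. The documents do not support that. In the table above no scenario exceeds 49%, ICC 0.01 gives about 20%, and at ρ = 1 the test is slightly conservative because a Poisson model overstates binomial variance.

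**Practice-level modifiers.** Simulated inflation is larger for these, and a reader might extend the point to practice deprivation. But section 11.3.3 refers to socioeconomic deprivation as patient-level data. The one practice-level modifier listed, implementation, is identified by a code from templates given only to intervention practices (section 10.4.1), so an interaction of that kind is not clearly estimable. No figure for practice-level modifiers is relied on here.

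**The analysis plan may settle it.** Section 11.3 defers to a SAP that is not shown, and nothing in the protocol excludes robust variance or further random terms. Nor does it say how a patient-level modifier enters a practice-scale model; two rows per practice is the natural reading, but it is a reading. This lowers the urgency. It does not remove the point, because the protocol states one random effect and says the interaction is added to that model, and following that text gives error bars that are too small.

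**Only additional and secondary analyses are affected.** This stands. A reader might infer that the primary result is at risk. It is not: in a separate simulation of this type of model the arm test rejected 6.7% of the time, close to nominal.

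**Conclusion.** The point holds as a structural weakness of moderate importance. As written, the interaction standard errors omit any variation in the subgroup PIP ratio between practices or PCNs, and are too small whenever such variation exists. Exact homogeneity across 500 PCNs is unlikely for prescribing data. For a patient-level modifier and ρ of 0.95 to 0.90, the plausible range is a standard error 1.5 to 2.9 times too small and 17 to 49% false positives at a nominal 5%, over ICCs of 0.01 to 0.04. Subgroup-specific baseline adjustment reduces the problem without removing it. The range is conditional on the assumed ρ, and it disappears at ρ = 1. It concerns the ≤6-medicines analysis and the other patient-level subgroups, not the primary comparison.

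**What to change.** State in section 11.3.3, or in the SAP, that all subgroup interaction estimates, intervals and tests use PCN-clustered robust standard errors. In the simulations this brought false positives back to about 5% in every scenario (1 to 9%, consistent with simulation error). An equivalent route is to compute each PCN's within-PCN log rate ratio between subgroups and compare these between arms at PCN level. Simulated rejection for that test was 4.9 to 5.8%. A random slope for the subgroup plus a practice-level random intercept addresses the same gap, but it was not checked by simulation. The text should also say how patient-level modifiers enter the practice-scale model and whether the baseline rate is subgroup-specific.

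No new data are needed and the primary analysis is unchanged. The cost is a sentence or two of wording and wider subgroup intervals.
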